#### **5.4.8. Study Drug Administration**

The study drug administration details including the administration date and time, dose, site of injection and comments will be presented in a by-subject listing.

The following parameters related to study drug administration will be summarized:

- Number of injections in the Treatment Period and in the Extension Period.
- Compliance percentage, calculated as [Number of injections]/[Planned number of injections]\*100%, where Planned number of injections is 7 for the Treatment Period and 18 for the Extension Period.
- Total rilonacept dose administered in the Treatment Period and in the Extension Period, defined as the sum of all doses (in mg) received by the subject in the corresponding period. For subjects receiving a fixed-dose regimen (e.g. 160 mg) it will be assumed that the entire planned dose was injected. For subjects receiving weight-adjusted dose (e.g. 2.2 mg/kg) their weight collected at Screening Visit 1 will be used to calculate the amount of the study drug received for the entire duration of the trial.
- Percentage of injections self-administered by the subject, defined as [Number of self-administered injections] / [Total number of injections received by the subject except the very 1st one that is always administered by the site personnel ] \* 100%.

The parameters above for the Treatment Period will be summarized descriptively for the safety population. Separately these parameters for the Extension Period will be summarized descriptively for the Extension Period population. The parameters over both Treatment Period and Extension Period will also be summarized for the safety population.

Additionally the number and percentage of subjects who self-administered all their injections (except the very 1st one that is always administered by the site personnel) will be presented for the Treatment Period, Extension Period and the entire study.

#### **5.4.9. Efficacy Analysis**

##### **5.4.9.1. CRP**

Samples for CRP assessment will be obtained and sent to the central laboratory at each visit. CRP levels will be summarized descriptively by visit. Change from baseline will also be summarized for all post-baseline scheduled visits. This analysis will be performed by study part, but also for pooled groups of Parts 1, 2 and 4 and Parts 3 and 5.

Number and percentage of subjects with normal CRP (defined as  $\leq 0.5$  mg/dL) as well as with CRP  $\leq 1$  mg/dL will be presented by visit.

A subject with abnormal baseline CRP level ( $>0.5$  mg/dL) will be considered to have a *persistent CRP normalization in the Treatment Period* if she/he has at least two consecutive normal CRP results in the Treatment Period with no abnormal results in the Treatment Period after these normal results.

Similarly, a subject will be defined to have a *persistent CRP normalization in the study* if she/he has at least two consecutive normal CRP results at any time after the baseline (in either the Treatment Period or the Extension period) with no abnormal results after these normal results.

Number and percentage of subjects with persistent CRP normalization in the Treatment Period and in the entire study will be presented. The denominator for percentages will be the number of subjects with abnormal CRP at baseline.

A summary of number and percentage of subjects in the following categories among those with normal CRP at baseline ( $\leq 0.5$  mg/dL) will be presented:

- who did not have abnormal post-baseline CRP ( $>0.5$  mg/dL)
  - in the Treatment Period
  - in entire study (Treatment and Extension Period combined)
- who did not have more than one abnormal post-baseline CRP ( $>0.5$  mg/dL)
  - in the Treatment Period
  - in entire study (Treatment and Extension Period combined)

The denominator for percentages will be the number of subjects with normal baseline CRP.

Time to CRP normalization will be defined only for subjects with abnormal CRP at baseline as the study day of the first visit when normal CRP is observed. For subjects who never achieve normal CRP this time will be censored at the day of the last available CRP assessment. Kaplan-Meier estimates of the median, 25% and 75% percentiles of time to CRP normalization will be provided with 95% confidence intervals (estimated using the method of Brookmeyer and Crowley with loglog transformation for the survival function, PROC LIFETEST in SAS).

#### **5.4.9.2. Echocardiogram**

Echocardiograms (ECHOs) including assessment of pericardial effusion will be performed at screening (SCV1), at Study Site/Clinic visits during the Treatment Period (Interval Evaluation Visit [if applicable] and Visit 7/End-of-Trial), at the Interval Evaluation Visit during the EP [if applicable], and at the Final Study Visit/Visit 8.

For the purposes of the analysis, the results of local ECHO evaluations at the site for presence or absence of pericardial effusion will be used.

Presence of pericardial effusion may include any size of pericardial effusion, and may range from trivial/trace/physiologic to very large.

Size of pericardial effusion, if available, will be noted in individual subject listings.

Number and percentage of subjects with pericardial effusion will be presented by visit.

A shift table will be created presenting shifts between presence and absence of the pericardial effusion from baseline to Visit 7 (end of Treatment Period) and Visit 8 (end of Extension Period). At each post-baseline visit the denominator for percentages will be the number of subjects with assessment of pericardial effusion at both baseline and the current visit.

These analyses will be performed on the mITT population.

At the end of or after the study, ECHO images may be assessed by a central reader.

#### **5.4.9.4. Pericarditis Manifestation**

Presence of pericardial rub will be assessed as part of physical examination at screening (SCV1 and SCV2), at Study Site/Clinic visits during the Treatment Period (Interval Evaluation Visit [if applicable] and Visit 7/End-of-Trial), at the Interval Evaluation Visit during the EP [if applicable], and the Final Study Visit/Visit 8. If applicable, assessment of pericarditis signs will also be performed at unscheduled visits.

Electrocardiographic signs of pericarditis, namely widespread ST-elevation or PR depression will be assessed as part of 12-lead ECG at screening (SCV1 and SCV2), at Study Site/Clinic visits during the Treatment Period (Interval Evaluation Visit [if applicable] and Visit 7/End-of-Trial), at the Interval Evaluation Visit during the EP [if applicable], and at the Final Study Visit/Visit 8, based on local site ECG assessment.

Fever will be assessed as part of vital signs at Study Site/Clinic visits. Fever will be defined as body temperature  $> 37.5$  degrees C.

Number and percentage of subjects with pericardial rub, widespread ST-elevation and PR depression based on local ECG read, with fever and with pericardial effusion per Echocardiogram based on a local read will be presented by visit. This analysis will be performed by study part, but also for pooled groups of Parts 1, 2 and 4 and Parts 3 and 5.

These analyses will be performed on the mITT.

#### **5.4.9.5. Magnetic Resonance Imaging (MRI)**

Cardiac MRI is an optional assessment for Parts 1, 3, 4 and 5 and may be performed at study entry (SCV1) and at the final study visit (Visit 8) to assess any changes in pericardial inflammation. For Part 2, cardiac MRI to determine subject's eligibility based on presence of pericardial inflammation is a mandatory assessment.

For the purposes of the analysis of treatment response in all subjects at the end of the study, all cardiac MRI images will be assessed by a central reader for presence or absence of inflammation

Number and percentage of subjects with following MRI parameters will be presented by visit:

- presence of pericardial inflammation as measured by pericardial delayed hyperenhancement (normal, mild, moderate, severe)
- presence of myocardial inflammation as measured by myocardial delayed hyperenhancement (yes/no)
- presence of pericardial effusion by category:
  - Trivial/Physiological
  - Small (<10 mm)
  - Moderate (10-20 mm)
  - Large (>20 mm)
  - Very large (>25 mm)

These analyses will be performed by study part, but also for pooled groups of Parts 1, 2 and 4 and Parts 3 and 5.

These analyses will be performed on the mITT population.

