**2.1.2. Secondary Objectives for Parts 1, 2 and 4**

- To explore the time course to improvement of pericarditis parameters in symptomatic subjects with RIP or recurrent PPS treated with KPL-914.
- To evaluate the effect of KPL-914 on pericardial inflammation based on cardiac MRI.
- To evaluate the safety of KPL-914 in symptomatic subjects with RIP or recurrent PPS.

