### **5. STATISTICAL METHODOLOGY**

#### **5.1. General Considerations**

All statistical evaluations will be conducted using SAS® version 9.4 or higher (SAS® Institute, Cary, North Carolina). All tables, figures and listings will be produced in landscape format.

Because of the small sample size no inferential statistical analyses or hierarchical testing are planned. Analysis will be descriptive in nature.

Each Part will be analyzed separately. Tables will have columns corresponding to or be stratified by study Parts. Select analyses, as specified in further sections, will be performed for pooled groups of Parts 1, 2 and 4 and Parts 3 and 5, representing similar RIP and PPS populations, i.e. symptomatic and asymptomatic-CS dependent subjects. In general, all data will be listed by study part, subject and visit/time point where appropriate. The total number of subjects under the stated population (N) will be displayed in the header of summary tables.

Data will be summarized using descriptive statistics for continuous variables. Unless otherwise specified, descriptive statistics will include number of subjects, mean, standard deviation, minimum, median and maximum. In case of  $n < 2$ , where  $n$  indicates the number of evaluable subjects at the particular time point, the standard deviation will not be calculated.. The statistic “Missing” will also be presented as the number of missing entries/subjects, if any

at that visit/timepoint, and presented as a summary statistic only when non-zero. The minimum and maximum statistics will be presented to the same number of decimal places as the original data. The mean and median will be presented to one more decimal place than the original data, whereas the standard deviation will be presented to two more decimal places than the original data.

In summary tables of categorical variables, counts and percentages will be used. The count [n] indicates the actual number of subjects with a particular value of a variable or event, which should always be less than or equal to the total number of subjects with non-missing value of the variable or event [M]. Percentage will be obtained by:  $\% = (n/M)*100$ . Unless otherwise stated, all percentages will be expressed to one decimal place.

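### MRI pericardial inflammation, a secondary objective in all Parts, is summarised only as unpaired percentages by visit, so a difference between baseline and Visit 8 in either direction can reflect who was rescanned

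*SAP*

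**What the plan says.** SAP Section 2.1.2 lists the secondary objective for Parts 1, 2 and 4: "To evaluate the effect of KPL-914 on pericardial inflammation based on cardiac MRI". Section 2.1.4 repeats it for Parts 3 and 5.

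Section 5.4.9.5 says who is scanned and when. "Cardiac MRI is an optional assessment for Parts 1, 3, 4 and 5", at study entry and "at the final study visit (Visit 8) to assess any changes in pericardial inflammation". For the remaining Part: "For Part 2, cardiac MRI to determine subject's eligibility based on presence of pericardial inflammation is a mandatory assessment". No mandatory follow-up scan is stated for any Part.

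The analysis in the same section is "Number and percentage of subjects with following MRI parameters will be presented by visit". The parameters are pericardial delayed hyperenhancement grade, myocardial delayed hyperenhancement and effusion category, by Part and for the two pooled groups. On the analysis set: "These analyses will be performed on the mITT population". No change from baseline, shift table or both-scans denominator is given.

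Section 5.1 divides each count by the number of subjects with a non-missing value, and restricts by-visit tables to scheduled visits. Section 2.2 places the final visit (Week 25) at the end of the Extension Period, which is optional and offered, at the investigator's discretion, to subjects judged to be responders.

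For echocardiographic effusion, Section 5.4.9.2 plans by-visit percentages and also a shift table from baseline to Visits 7 and 8, in which "the denominator for percentages will be the number of subjects with assessment of pericardial effusion at both baseline and the current visit".

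**The concern.** The objective and the stated purpose of the scans are both about change within subjects. The planned summary gives two cross-sectional percentages. The baseline figure covers everyone scanned at entry. The Visit 8 figure covers those who were judged responders, entered the extension, reached its end and had a second scan.

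A reader will subtract one percentage from the other and take the result as the effect of treatment on inflammation. With about 40 subjects over five Parts and mostly optional scanning, a few absent second scans can move the Visit 8 percentage appreciably. What is at stake is the reading of a named secondary objective.

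**Working it through.** The SAP states no MRI figure and its sample size is empirical (Section 3.1), so there is no planned number to reproduce. The check asks how far the by-visit percentages can differ when no subject's inflammation status changes.

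**Inputs from the SAP**
- Denominator: subjects with a non-missing value at that visit (Section 5.1).
- Scans: entry and Visit 8 only (Section 5.4.9.5).
- Follow-up scan not mandatory; Visit 8 follows an optional extension (Sections 5.4.9.5 and 2.2).

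**Assumed inputs, not in the SAP**
- Baseline prevalence of inflammation among those scanned: 70% or 50%.
- Rescan rates by baseline status, varied between 30% and 80%.
- True within-subject change: none.

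**Formula**

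Visit 8 % = (inflamed at baseline × their rescan rate) / (inflamed × their rate + non-inflamed × their rate)

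**Results for 20 subjects scanned at baseline** (fractional counts are expected values)

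| Inflamed / not at baseline | Rescan rate, inflamed / not | Visit 8 calculation | Visit 8 % | Apparent change (points) |
|---|---|---|---|---|
| 14 / 6 (70%) | 50% / 50% | 7 / (7 + 3) | 70.0 | 0 |
| 14 / 6 | 50% / 80% | 7 / (7 + 4.8) | 59.3 | −10.7 |
| 14 / 6 | 30% / 80% | 4.2 / (4.2 + 4.8) | 46.7 | −23.3 |
| 14 / 6 | 80% / 50% | 11.2 / (11.2 + 3) | 78.9 | +8.9 |
| 10 / 10 (50%) | 50% / 50% | 5 / (5 + 5) | 50.0 | 0 |
| 10 / 10 | 50% / 80% | 5 / (5 + 8) | 38.5 | −11.5 |
| 10 / 10 | 30% / 80% | 3 / (3 + 8) | 27.3 | −22.7 |
| 10 / 10 | 80% / 50% | 8 / (8 + 5) | 61.5 | +11.5 |

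A table restricted to subjects with both scans gives a change of 0 in every row.

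**Whole-number example.** Suppose 14/20 are inflamed at entry and 10 are rescanned, of whom 5 were inflamed at entry and 5 are inflamed at Visit 8. The by-visit table reads 70% then 50%. The ten not rescanned were 9/10 inflamed at entry (14 − 5 = 9). Net paired change: 5/10 against 5/10, or zero.

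**Part 2 alone.** Section 2.1 requires pericardial inflammation on MRI, confirmed by the imaging core lab, at entry. Baseline presence is therefore about 100% whichever subset is rescanned, and loss of subjects cannot create a fall in presence. The mild, moderate and severe mix can still shift with who returns.

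**Pooled Parts 1, 2 and 4.** Because Part 2 enters at about 100%, a change in its share of scanned subjects between the two visits also moves the pooled percentage without any change within a Part.

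**The case against.** The strongest reply has four parts.

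1. *The data are not hidden.* Section 5.1 generally provides by-subject listings, and with so few subjects the pairs can be traced by hand. True, but a listing is not a summary, and none of the planned MRI summaries reports change.
2. *By-visit percentages are an ordinary format in this SAP.* Rub, ECG signs and fever are handled the same way in Section 5.4.9.4, so the echocardiography shift table is an addition and not a rule that Section 5.4.9.5 breaks. This is fair. MRI inflammation differs in being named in the objectives and in having a single, non-mandatory follow-up scan.
3. *The study is a descriptive pilot.* Section 5.1 plans no inferential analysis, and the primary objectives concern variability and steroid weaning. This stands, and it limits the consequence.
4. *The figures are hypothetical.* They are. They show what the planned summary cannot exclude and do not predict what will occur.

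A reader might go further and infer that the by-visit comparison is biased in favour of the drug. The SAP does not support that. A changing denominator lowers the Visit 8 percentage only if subjects inflamed at entry are rescanned less often, and nothing in the SAP says so; sites that prefer to rescan an abnormal first scan would produce the opposite. Offering the extension to responders is a separate selection. It plausibly favours the drug, but pairing does not remove it, because subjects with both scans are still responders.

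**Conclusion.** The point holds as an avoidable weakness in how a secondary objective is summarised. In Parts 1, 3, 4 and 5, in the pooled groups and in the grade distribution, a difference between the baseline and Visit 8 percentages in either direction can arise from who was rescanned.

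Under the assumptions tabulated (no true change, baseline prevalence 50% or 70%, rescan rates of 30% to 80%), the apparent fall is about 11 to 23 points or the apparent rise about 9 to 12, with no distortion when rescanning is unrelated to baseline status. The absence of a planned paired MRI summary is certain from the text; the size of any distortion is not.

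Two stronger readings should be resisted. Presence of inflammation in Part 2 alone is not exposed to this mechanism. Nor will a paired table yield an effect estimate for all treated subjects, since it describes those who responded and completed the extension. No test, decision rule or sample size depends on MRI, so the consequence is limited to misreading a descriptive secondary result.

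**What to change.** Add to Section 5.4.9.5 a shift table from baseline to Visit 8 for pericardial inflammation, by presence or absence and by delayed hyperenhancement grade, for each Part and for the two pooled groups. Take as denominator the subjects with both scans, following Section 5.4.9.2. By Part the grade table will be sparse, so presence or absence in the pooled groups is likely to be the most readable panel.

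Report beside it the number scanned at baseline only. Add a sentence saying that Visit 8 scans represent subjects who responded and completed the extension, and that pairing does not remove this selection. The by-visit percentages can stay.

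Cost: one extra table and a sentence, from central reads already planned. No new scans, visits or data are needed.

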#### **5.4.9.6. Quality of Life**

A validated Quality of Life Questionnaire PROMIS Scale v.1.2-Global Health will be used to assess changes in the subject's physical and mental well-being. The subject will fill the PROMIS questionnaire at screening (SCV1), at Visit 1 (Day 0), at the Interval Evaluation Visit (Week 3-4), at the end of the Treatment Period (Visit 7/End-of-Trial), at the Interval Evaluation Visit during the EP, and at the Final Visit (Visit 8).

Responses to each of the QoL questionnaire questions will be summarized descriptively by visit and question. Change from baseline will also be summarized for post-baseline scheduled visits.

Additionally, Global Physical Health and Global Mental Health scores will be calculated as described in Appendix 8.3. These scores will also be summarized descriptively by visit along with their change from baseline.

This analysis will be performed by study part, but also for pooled groups of Parts 1, 2 and 4 and Parts 3 and 5 on the mITT population.

#### **5.4.9.7. Correlation Analysis**

Correlations between CRP levels and pericardial 11-point Numerical Pain Rating Scale will be explored graphically. A scatter-plot will be created for each Study Part separately with X-axis representing CRP level and Y-axis representing pericardial pain NRS. Data points from all subjects of the Study Part from all available visits will be used. The regression line will be superimposed on the scatter-plot, and the regression equation with the  $R^2$  coefficient will be presented.

Relationship between CRP levels and presence of pericardial effusion per Echocardiography local read will also be explored. For each study part and each visit when Echocardiogram is performed CRP levels will be summarized descriptively separately side-by-side for the subjects with pericardial effusion and subjects without pericardial effusion. A p-value from the two-sample t-test comparing the CRP levels between these two groups will be provided.

These analyses will be performed on the mITT population.

#### **5.4.9.8. Prednisone Use**

The following characteristics of prednisone use throughout the study will be summarized descriptively. Prednisone use will be identified via medical review of baseline and concomitant medications.

- Daily dose of prednisone at study baseline (mg/day) in subjects who were treated with study drug in TP and who were taking prednisone at baseline
- Daily dose of prednisone at the start of extension period (mg/day) in subjects who were treated in EP with study drug and received prednisone at EP start
- For each subject with prednisone use at baseline, the subject's average daily dose in the Treatment Period (mg/day), defined as total cumulative dose of prednisone taken in the Treatment Period divided by the duration of the Treatment Period in days. For the purposes of this analysis the Treatment Period ends on the day of Week 6/End of Trial/Visit 7 for subjects who proceed to the Extension Period; for subjects who do not enter the Extension Period, the Treatment Period ends on the day of the last study drug dose.
- For each subject with prednisone use at the start of the extension period, the subject's average daily dose in the Extension Period (mg/day), defined as total cumulative dose of prednisone taken in the Extension Period divided by the duration of treatment in the Extension Period in days. For the purposes of this analysis the Extension Period starts on the day of Week 6/End of Trial/Visit 7.
- For each subject with prednisone use at baseline, the subject's average daily dose in the Treatment and Extension Periods combined (mg/day), defined as total cumulative dose of prednisone taken in both the Treatment and Extension Periods

divided by the duration of periods in days (from the first dose in the Treatment Period to the last dose in the Extension Period).

This analysis will be performed by study part, but also for pooled groups of Parts 1, 2 and 4 and Parts 3 and 5.

To evaluate disease activity after discontinuation of corticosteroids, selected efficacy parameters including CRP will be analysed in subjects who received prednisone at baseline and discontinued it by the end of EP.

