## **2. STUDY DETAILS**

### **2.1. Study Objectives**

The study is comprised of 5 Parts.

- Part 1 enrolls symptomatic subjects with recurrent idiopathic pericarditis (RIP) with an elevated marker of systemic inflammation (C-reactive protein [CRP]  $> 1\text{mg/dL}$ ).
- Part 2 enrolls symptomatic subjects with RIP with CRP  $\leq 1\text{ mg/dL}$  which, in the opinion of the investigator, can be attributed to concomitant medications (e.g., corticosteroids) and with pericardial inflammation present on cardiac magnetic resonance imaging (MRI) confirmed by the imaging core lab.
- Part 3 enrolls subjects with corticosteroid-dependent RIP not experiencing symptoms which would meet the diagnostic criteria for a flare of pericarditis.
- Part 4 enrolls symptomatic subjects with recurrent post pericardiotomy syndrome (PPS) with an elevated marker of systemic inflammation (CRP  $> 1\text{mg/dL}$ ).
- Part 5 enrolls subjects with corticosteroid-dependent recurrent PPS not experiencing symptoms which would meet the diagnostic criteria for a flare of pericarditis.

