**2.1.3. Primary Objective for Parts 3 and 5**

- To evaluate feasibility of weaning from corticosteroids while receiving KPL-914 in subjects with corticosteroid-dependent RIP or recurrent PPS.

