**Extension Period (EP):** The EP is defined as the 18 weeks following the Treatment Period. Subjects who are considered to be “Treatment Responders” will be, at the discretion of the Investigator, offered participation in an optional 18-week EP, in which weekly administration of open-label KPL-914 may be continued for a total duration of 24 weeks. The weekly KPL-914 doses will be by self-administration or administered by adequately trained caregiver, and study nurse visits to the subject’s home as well as Investigator (or designee) telephone calls/virtual visits will continue on a monthly basis. During the EP, the Investigator is encouraged to wean concomitant NSAIDs, and/or colchicine, and/or corticosteroids. It is encouraged that NSAIDs and colchicine be tapered and withdrawn within 15 days after entry into the EP. It is encouraged that corticosteroids be progressively tapered (e.g., by 5 mg prednisone or equivalent every week in adults or 0.2mg/kg every week in subjects <18yo) and discontinued within 6 weeks after entering to EP (i.e., by Study Week 12) unless in the opinion of Investigator, a different corticosteroid weaning schedule is required based on subject’s clinical status. Other pericarditis medications may also be initiated at the discretion of the Investigator. All changes to pericarditis-related medications should be captured in the source records and eCRF

Unscheduled clinic visits can be scheduled any time as determined by the Investigator/upon subject request. In addition, Investigators are encouraged to schedule subjects at the Study Site/Clinic for an in-person Interval Evaluation Visit between Weeks 15 to 20 (8 to 13 weeks after Visit 7) to assist the Investigator in the clinical management of the subject. During this visit a physical examination, vital signs, ECG, echocardiogram, and laboratory testing can be performed. However, this visit is not mandatory, and therefore not all subjects will have it.

Subject-reported pericardial pain evaluations using a validated 11-point NRS instrument as well as AE monitoring will be performed during the EP at on-site clinic visits and/or during monthly Investigator (or designee) phone calls/virtual visits. A subject-reported QoL questionnaire will be administered at the Interval Evaluation Visit and the Final Visit of the EP. At the end of the EP, subjects will complete the Week 25/Final Visit.

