##### **4.2. Primary Efficacy Endpoints for Parts 3 and 5**

Primary efficacy endpoint will be disease activity after corticosteroid taper in subjects with corticosteroid dependent RIP or recurrent PPS.

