#### **5.4.9.9. Concomitant Pericarditis Medications**

Pericarditis medications will be identified among subjects' concomitant medications and classified as analgesics, aspirin, NSAIDs, colchicine or corticosteroids through medical review.

For the purposes of these analyses, medications taken on as needed basis (PRN) will not be accounted for due to difficulty in assessing the actual dose. Only medications with a fixed daily use frequency (QD, BID, TID, etc.) will be used, so that their daily dose can be calculated.

For the purposes of these analyses, the Treatment period ends and the Extension Period starts on the day of Visit 7 for subjects who proceed to the Extension Period. For subjects who do not enter the Extension Period, the Treatment Period ends on the day of the last study drug dose.

Each category of pericarditis medications will be analyzed for changes in the Treatment Period, Extension Period and the study as a whole as follows and categorized as follows:

1. New Medication: a new medication of the given category is taken at the end of the period compared to the start of the period.
2. Dose Increase: no new medications of the given category are taken, but the total daily dose of one of the medications increased by the end of the period compared to the start of the period.
3. Dose Decrease: there are no new medications and no dose increases, and the total daily dose of one of the medications decreased by the end of the period compared to the start of the period.
4. Stopped: a medication of the given category was taken at the start of the period, and none is taken at the end of the period.
5. Stable Dosing: none of the above.

Number and percentage of subjects with each of the above outcomes will be presented by the pericarditis medication category and study period (Treatment, Extension and study as a whole). The population will be mITT for the Treatment Period and EP for the Extension

Period and the study as a whole. The denominator for percentages for the “New Medication” outcome will be the total number of subjects in the appropriate population. For all other outcomes it will be the number of subjects who take any medication of the given category at the start of the period.

This analysis will be performed by study part, but also for pooled groups of Parts 1, 2 and 4 and Parts 3 and 5.

Use of Pain/Rescue medications will be also analysed (see section 5.4.10.7).

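### Section 5.4.9.8 aims at disease activity after corticosteroids are stopped, but defines its subject set and all five dose summaries by prednisone alone, so its steroid status can contradict that in section 5.4.9.9

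*SAP*

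**What the plan says.** The SAP frames the question for Parts 3 and 5 by drug class throughout.

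- Section 2.1 on enrolment: "Part 3 enrolls subjects with corticosteroid-dependent RIP not experiencing symptoms", and "Part 5 enrolls subjects with corticosteroid-dependent recurrent PPS not experiencing symptoms".
- Section 2.1.3, the primary objective: "To evaluate feasibility of weaning from corticosteroids while receiving KPL-914 in subjects with corticosteroid-dependent RIP or recurrent PPS".
- Section 4.2, the primary endpoint: "Primary efficacy endpoint will be disease activity after corticosteroid taper in subjects with corticosteroid dependent RIP or recurrent PPS".
- Section 2.2, on the Extension Period (EP), gives an example of an encouraged taper, "by 5 mg prednisone or equivalent every week in adults", so steroids other than prednisone are allowed for.
- Section 5.4.2 lists systemic corticosteroids, as a class, among the baseline pericarditis medications.

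Section 5.4.9.8 narrows this to one drug. Medical review is to identify prednisone use. Five dose summaries follow, each restricted to subjects on prednisone at baseline or at the start of the EP, and each in mg/day of prednisone. The section closes with an analysis whose purpose is given as "To evaluate disease activity after discontinuation of corticosteroids", for which "selected efficacy parameters including CRP will be analysed in subjects who received prednisone at baseline and discontinued it by the end of EP".

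Section 5.4.9.9 returns to the class. For each category, corticosteroids among them, it sorts subjects by how their medication changed over a period. New Medication means that "a new medication of the given category is taken at the end of the period compared to the start of the period". Stopped requires that something in the category was taken at the start and nothing in it at the end.

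**The concern.** The closing sentence of 5.4.9.8 states its purpose for a drug class and selects its subjects by a single drug. The two agree only if every steroid-treated subject takes prednisone and nothing else, which the SAP does not require.

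Where they differ, two kinds of error follow. A subject still taking a corticosteroid can enter the set meant to show the disease without corticosteroids. That would tend to favour apparent stability: section 2.1 itself, in describing Part 2, accepts that low CRP may be attributable to concomitant medications such as corticosteroids. In the other direction, a subject who was truly weaned, but from a different steroid, is lost from the set. Both errors touch the question that Parts 3 and 5 were set up to answer.

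**Working it through.** The SAP gives no figure to reproduce here: the analysis is descriptive (section 5.1) and the sample size was set empirically (section 3.1). The check is to apply the rules of 5.4.9.8 and 5.4.9.9 to the same subjects. I assume fixed-frequency dosing and membership of the EP population, as 5.4.9.9 requires for its whole-study analysis.

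| Subject | 5.4.9.8, post-discontinuation set | 5.4.9.8, dose summaries | 5.4.9.9, corticosteroids, whole study |
|---|---|---|---|
| A. Prednisone at baseline and at EP start; switched in the EP to another systemic corticosteroid, still taken at the end | Included | In all five; 0 mg/day after the switch in the averages that span it | New Medication, so not Stopped |
| B. Another systemic corticosteroid at baseline, never prednisone; none at the end of the EP | Excluded | In none | Stopped |
| C. Another systemic corticosteroid at baseline, prednisone by EP start; none at the end of the EP | Excluded (no prednisone at baseline) | Only in the two keyed to EP start | Stopped |

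For A and B the two sections give opposite answers on whether the subject came off corticosteroids. C shows that exclusion from every dose summary applies only to subjects never on prednisone.

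**Dose averages.** Let subject A take prednisone at d mg/day for a fraction f of the period, then switch. The reported average is d × f + 0 × (1 − f) = d × f. If the equivalent dose stays the same after the switch (assumption), the total corticosteroid average is d, and the summary understates it by d × (1 − f). That is nothing with no switch (f = 1) and approaches the whole dose for a very early switch.

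**Weight of one subject.** Section 3.1 gives approximately up to 40 subjects over five Parts. An even split (assumption; the SAP states none) gives 40/5 = 8 per Part and 2 × 8 = 16 for Parts 3 and 5 pooled. One subject is then 1/8 = 12.5% of a Part or 1/16 = 6.25% of the pool. The post-discontinuation set is a subset of these, so a subject wrongly included weighs at least that much in it. These are shares of an assumed denominator, not shifts in CRP or any other result.

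**Text that might rescue the rule.** No sentence in 5.4.9.8 extends prednisone to equivalents, and no conversion is given anywhere in the SAP. Section 5.4.9.9 counts medication changes and reports no CRP, pain or other disease activity, so it cannot stand in for the post-discontinuation analysis.

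**The case against.** The strongest reply is that little is lost. A Part 3 or Part 5 subject on another steroid still appears in the mITT summaries of CRP, NRS, pericarditis manifestations, recurrent episodes and Clinical Response. Section 2.2 encourages steroid discontinuation by Study Week 12, so the later EP and Visit 8 results already bear on activity after taper. Section 5.4.9.9 gives a correct class-level count of subjects who stopped, by Part and pooled, for fixed-frequency use, and the by-subject medication listings would reveal a switch. The wording about equivalents sits inside an example: it permits other steroids but does not show that any were used. Medical review might also treat equivalents as prednisone in practice.

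Much of this stands, and it limits the reach of the point. A reader might infer that non-prednisone subjects drop out of the Parts 3 and 5 primary endpoint. The SAP does not support that: it nowhere labels the closing analysis of 5.4.9.8 as primary, and the subjects remain in the summaries just listed. A reader might also infer that a switched subject counts as steroid-free throughout the SAP; that is so only within 5.4.9.8. Nor is the New Medication rule in 5.4.9.9 an error. It is a stated convention, and judging that category on total equivalent dose would be a preference.

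The mismatch within 5.4.9.8 remains. The by-visit mITT summaries are not conditioned on taper or discontinuation, and a programmer following the text would not include equivalents.

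**Conclusion.** The concern holds for section 5.4.9.8. Its stated purpose and its selection rule differ, and followed literally the rule can put a subject still on steroids into the post-discontinuation set and leave a weaned subject out. It is also the only visible analysis whose stated purpose matches the endpoint in section 4.2. That link is an inference from the wording; section 4.3 is redacted and the protocol is not at hand.

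The size is unknown. The SAP does not say how many subjects took a steroid other than prednisone, and if none did the effect is zero. With so few subjects per Part, one or two could matter, but the shares of 12.5% and 6.25% should not be read as an estimated bias. In an open-label descriptive pilot without inferential testing, this should be fixed but does not undermine the plan as a whole.

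**What to change.** In section 5.4.9.8:

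- define baseline use as use of any systemic corticosteroid, and discontinuation as no systemic corticosteroid at the end of the EP, consistent with the class in 5.4.9.9;
- give the five dose summaries in prednisone-equivalent mg/day, using one conversion table fixed in the SAP, for subjects on any systemic corticosteroid at the relevant start point.

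Section 5.4.9.9 needs no change. The cost is a few lines of SAP text and one table, since the medical review of medications is already planned. The small downside is that the conversion is approximate. The change concerns analysis definitions only and leaves every dose and taper in the study as it is.
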